3.7. Summary

Although smoking rates have declined in the overall US population, there has been little to no decline among people with ADs. A nicotine reduction strategy for combustible tobacco combined with e-cigarette availability may have complementary effects on smoking reductions and consequent tobacco-related health effects in this vulnerable population. This research is highly significant because it will model how the availability of e-cigs, a non-combusted nicotine product that is rapidly increasing in use among US smokers, impacts the effectiveness of a reduced-nicotine policy for cigarettes in this vulnerable population. It is responsive to the goals of the FDA in that the study conditions are designed to model real-world scenarios of possible harm reduction policies in a population that is vulnerable to smoking persistence.

4. Project Study Methods

This study will use a four-condition, parallel-groups research design. After a baseline period in which daily smoking rate and other baseline assessments are completed, participants will be randomly assigned to one of the following four conditions for a 16-week experimental period: (1) normal nicotine content cigarettes (NNCCs, 15.8 mg/g) alone, which serves as the control condition; (2) very low nicotine content cigarettes (VLNCCs, 0.4 mg/g) alone; (3) VLNCCs + tobacco-flavored nicotinized e-cigs (TF e-cig, 4.8 - 5.0% nicotine by weight, NBW, if they choose to use the Vuse or JULL devise, respectively); or (4) VLNCCs + preferred-flavor nicotinized e-cigarette (PF e-cig).

5. Study Screening Procedures

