This study will use a one-week, two-session baseline period to collect baseline individual difference measures and monitor daily usual-brand smoking behavior. At Baseline 1 or within 1 business day of the Baseline 1 visit, participants will be provided their usual brand cigarettes to smoke, equivalent to 150% of their daily smoking rate. Participants will be encouraged to come to the lab to pick up their usual brand cigarettes in a curbside exchange after they complete the questionnaires and physio for the BL1 visit. Those who cannot come to the lab will receive product via a commercial courier. A time line follow back (TLFB) will be used during the period between Baseline 1 and Baseline 2 to assess the daily cigarette use for the first 7 days the participant has product. The participant must have received their UB cigarettes from the lab before the 7-day assessment period starts, and Baseline 2 must occur at least 7 days after the participant receives their usual brand cigarettes from the lab. If the baseline period extends past seven days and if the participant has run out of product, participants will need to purchase their own usual brand cigarettes. Use of a two session baseline period will ensure stability of daily smoking reports, reduce reactivity to the daily cigarette monitoring, and reduce participant burden. During the two baseline sessions, participants will complete subjective questionnaires. Each visit will last approximately two to four hours. At the end of each baseline session, the researcher will complete the End of Visit Evaluation Form,. This will allow the researcher to make note of any problems encountered during the visit and to assess the truthfulness of the participant in regards to self-report of tobacco use. Participants will also be supplied with saliva test equipment and urine collection equipment during the Baseline 1 product exchange so that they can collect saliva and first void urine samples during the Baseline 2 visit.

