For the Baseline 1 visit and all subsequent visits, the participant will be sent a REDCap link within 15 minutes of the start of the scheduled visit to complete all of the non-interviewer administered questionnaires. The participant will complete these questionnaires on their own but can have the research assistant present on a video call if they desire. Before beginning the physiological assessment portion of the visit over video call, the research assistant must review the participant's questionnaire responses for that visit. Participants will be compensated after the completion of the study visit and when the participant has received their new product.

At Baseline 2 and all subsequent visits, after the participant has answered the questionnaires and has completed the physiological portion of the visit over video call, participants will be asked to come to the lab for exchange of product and biological samples. Participants will bring in their used and unused product from the previous visit as well as a first-void urine sample for assessing tobacco-related toxin exposure and a salivary sample for assessing nicotine metabolism rate on applicable visits (BL2, Week 8 and Week 16) using equipment that was provided at the previous visit. Participants will be instructed to call the RA at the office when they get to the clinic to ensure that there is enough space in the smoking chambers to house all participants while abiding by safety guidelines as detailed on page 14 of the protocol. All participants must pass a COVID19 screening before entering the building. When invited into the lab, the participant will be shown to a smoking chamber and will instructed to place their bag of product outside of the chamber. The participant will wait here while the RA processes and returns product through the randomization database. Then the RA will dispense new product and bring the bag back to the participant. When the RA deems it safe for the participant to exit the chamber, the RA will instruct the participant that they can leave. The RA will instruct the participant to observe social distancing measures during this exchange, providing clarification if necessary. If a participant forgets their first-void urine sample at the Baseline 2 visit, staff will ask participant to come back to the clinic with their first void urine sample before exchange of product occurs. If participant is unable to return to the clinic with their first void

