sample, staff can arrange to meet the participant off campus to pick up their urine sample and to give participant their study product. Distancing and safety measures as described above must be observed. For participants who cannot make it to UHC, special arrangements will be made to enable use of the randomization database and product return/distribution procedures to the extent possible. Each week, during - or scheduled as nearly as possible to – a virtual visit, a complete accounting of the participant's product inventory will be taken and processed remotely through the randomization database. The participant will separate product based on its type (e-cigarette or combustible inventory) and status (used/unused), and the RA will process return characteristics through the database accordingly. The RA will clarify barcode characteristics with the participant when legibility is compromised. The participant will be instructed to keep unused product in their possession, but to exchange any used product with the courier who will deliver newly dispensed replacement products within 48 hours.

Product that will be given to participants for the Baseline 2 visit cannot be given/sent to participants until 7 days have passed following completion of the Baseline 1 visit. We will need to calculate baseline smoking rate during this 7-day period and so participants cannot have access to any blinded study product or e-cigarettes before this 7-day period has ended.

6.1. Visit scheduling requirements for baseline period:

Participants will be required to schedule the Baseline 1 visit within 30 days of the completion of their screening visit. If a participant still wants to be in the study after 30 days, he/she will need to be re-screened. The participant will need to be re-consented but will maintain the original REDCap Subject Identifier. The ideal target window separating Baseline 1 and Baseline 2 is between 7 and 12 days. The minimum is 7 days and the maximum is 21 days. If the participant does not complete the visit within 21 days, then he/she will not be rescheduled and will be discontinued from the study.

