Participants in the e-cigarette conditions will be given e-cigarette pods BEFORE the training session occurs. These pods will be either picked up at the lab (preferred) or delivered to the participant 1 to 2 days before their Baseline 2 visit occurs. Participants randomized to the e-cigarette conditions will be notified before their Baseline 2 visit (but after the 7-day period following Baseline 1) and informed of their e-cigarette condition. Participants randomized to the flavored condition will be given pods of up to three flavors of their choice. Staff will calculate how many total pods participants will be given at this time based on their smoking rate, and participants will be able to choose the proportion of each flavor that they would like to receive.

The e-cigarette training session will occur over video chat after the physiological measurements have been collected. The first 30 minutes of the training session will consist of the participant being taught how to use, charge, and replace pods/cartridges for their e-cigarette of choice. Participants will first try their JUUL using the tobacco flavor, and then decide which device they would like to use for the duration of the study. If desired, participants are able to choose a preferred device to use without testing both e-cigarettes. At this point, participants who are in the tobacco-only flavor condition will conclude their training session.

For all visits following Baseline 2, participants in the preferred flavor condition are permitted

to take up to three flavors home per week, but can choose to take less than three flavors if desired. Participants will take home their chosen pods or cartridges of up to three flavors until next visit. Participants will be able to change their flavors at only one point in the study if they desire. Participants will only be allowed to take home three flavors at one time. Participants will be given an E-cigarette instructional manual that reviews the e-cigarette training done at this visit. Participants will be encouraged to call with any device issues.

6.4. Interactive Voice Response System:

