9.1 Statistical Methods

Continuous outcomes will be summarized by mean, standard deviation, median and range. Categorical outcomes will be summarized by frequencies and percentages. Skewed continuous outcomes will be log- or square-root transformed as appropriate. Variables measured at each baseline visit will be averaged and the average will be used as the baseline measurement. As we expect conditions to be balanced on important baseline characteristics due to randomization, our primary analysis for all endpoints will not be adjusted for potential confounders. However, a secondary analysis will be completed for all outcomes adjusting for demographic characteristics (e.g., age), that we have found to be important in prior studies. Potential moderators (e.g., SSRI vs. non-SSRI antidepressant, depression vs. anxiety disorders, BMI above or below 30) will be explored by adding that term and the moderator-by-condition term to the model. We will examine age group and gender as potential moderators in a similar fashion.

Participants will be randomized in equal probability to one of the four conditions, with randomization stratified by site and menthol cigarette status. All analyses will follow the intent-to-treat principle (i.e. subjects will be analyzed according to condition assignment, regardless of compliance). The Primary Aim will examine the effects of condition on total CPD (study product and non-study product). CPD will be analyzed by week (mean over all days in a seven-day period) using a mixed model to account for repeated measures from the same individual.

Models will include baseline CPD as a covariate. Using a mixed model also allows us to include the effect of study site as a random effect. Additional analyses conducted using data collected at the end of the study will use orthogonal comparisons to test for a linear trend in the decrease in CPD, such that VLNCC + PF e-cig > VLNCC + TO e-cig > VLNCC > NNCC, with

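### Both e-cigarette arms learn their condition and receive pods before Baseline 2, which still counts as baseline; Aim 2 e-cigarette contrasts may be biased if the models adjust for it

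*Combined protocol and SAP*

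**What the plan says.** Section 6.3 (e-cigarette training) sets the timing for the two e-cigarette arms: "Participants randomized to the e-cigarette conditions will be notified before their Baseline 2 visit (but after the 7-day period following Baseline 1"). Their pods are picked up at the lab, which is preferred, or "delivered to the participant 1 to 2 days before their Baseline 2 visit occurs". The device lesson comes later: "The e-cigarette training session will occur over video chat after the physiological measurements have been collected". Nothing comparable is stated for the NNCC or VLNCC-alone arms.

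Other sections describe a different order. Section 4: "After a baseline period in which daily smoking rate and other baseline assessments are completed, participants will be randomly assigned". Section 6 puts the Baseline 2 product exchange at the lab "after the participant has answered the questionnaires and has completed the physiological portion of the visit over video call".

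On the analysis side, Section 9.1 states: "Variables measured at each baseline visit will be averaged and the average will be used as the baseline measurement". It names baseline CPD as the covariate of the primary model and says that Aim 2 and the subjective outcomes will be handled similarly. CO, the usual-brand Cigarette Purchase Task, WISDM, QSU, MNWS, PANAS, BDI and OASIS are taken at both baseline visits (Section 6.2). Biomarker urine is collected at Baseline 2, Week 8 and Week 16 only.

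For the smoking-rate baseline there is an explicit lock, in Section 6: "participants cannot have access to any blinded study product or e-cigarettes before this 7-day period has ended".

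**The concern.** A baseline covariate should not be able to respond to assignment. Here it can, in two of four arms, because those participants know their condition, and may hold their pods, when Baseline 2 is measured. E-cigarette assignment is not blinded (Section 8.1). The plan does not exclude Baseline 2 from the average, tell participants to leave the pods unused until the visit, or ask whether they did. The 7-day lock shields CPD but was not extended to the other measures.

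At stake are the Aim 2 contrasts that involve an e-cigarette arm: comparisons with NNCC or VLNCC-alone, the linear trend and both threshold contrasts in Section 9.1. Randomization does not remove such a bias, and a larger sample does not shrink it. If Baseline 2 moves in the direction of the expected benefit, the effect is understated; if it moves the other way, the effect is overstated.

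**Working it through.** **The plan's own figure.** Section 9.2 uses an effect of 0.60 SD, 80% power, two-sided 0.05 and 15% loss. A two-sample t-test with 45 evaluable per arm has 80.4% power, and 45 / 0.85 = 52.9, rounded up to 53. This reproduces the stated 53 per condition, so I use n = 45.

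**Which measures are exposed**
- Baseline 2 has weight 1/2: CO, purchase task, WISDM, craving, withdrawal, mood.
- Baseline 2 has weight 1: NNAL, PAHs and the other urine biomarkers.
- Essentially protected: baseline CPD, taken from the first 7 days (Sections 6 and 8.2). A small overlap is possible, because Section 6 starts the 7-day diary when usual-brand cigarettes arrive, up to one business day after Baseline 1, whereas the lock counts from Baseline 1.
- Not exposed: FTND, whose only pre-treatment value is at screening (Section 5.4).

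Self-report can react to disclosure alone. CO and urine move only if smoking or vaping changes before the sample.

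**Bias.** An adjusted contrast is the difference in outcome means minus slope times the difference in baseline means. Take unit variances, equal correlation rho between Baseline 1, Baseline 2 and Week 16, and a shift delta at Baseline 2 in both e-cigarette arms. Neither rho nor delta is in the documents. I assume rho 0.5 to 0.7 and delta 0.1 to 0.3 SD.
- Baseline 2 only: slope rho, so b = rho × delta. This runs from 0.5 × 0.1 = 0.05 to 0.7 × 0.3 = 0.21 SD. Residual variance is 1 − rho², 0.75 to 0.51.
- Average of two visits: slope 2rho/(1 + rho), shift delta/2, so b = rho × delta/(1 + rho). This runs from 0.05/1.5 = 0.03 to 0.21/1.7 = 0.12 SD. Residual variance is 1 − 2rho²/(1 + rho), 0.667 to 0.424.

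SE = sqrt(residual variance / 45 × sum of squared weights). Trend weights are (−3, −1, 1, 3)/20.

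| Contrast | Bias | Sum of squared weights | Averaged, in SE | Urine, in SE |
|---|---|---|---|---|
| E-cigarette arm vs NNCC or VLNCC-alone | b | 2 | 0.19–0.90 | 0.27–1.39 |
| NNCC vs two e-cigarette arms | b | 1.5 | 0.22–1.04 | 0.32–1.61 |
| NNCC vs three VLNCC arms | 2b/3 | 1.333 | 0.16–0.74 | 0.22–1.14 |
| Linear trend per step | 0.2b | 0.05 | 0.24–1.14 | 0.35–1.76 |

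The bias is zero for NNCC vs VLNCC-alone, and for PF vs TF if both arms shift equally.

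**Simulation check.** In a four-arm ANCOVA with no true effects (20,000 replicates), pairwise bias at (rho, delta) = (0.5, 0.1) and (0.7, 0.3) was 0.050 and 0.210 for Baseline 2 only, 0.034 and 0.123 for the average, and under 0.001 for Baseline 1 alone. In a two-arm simulation with a true effect of −0.60, rho 0.5 and a −0.3 SD shift, the estimates were about −0.45 (urine; power 66% instead of 89%) and −0.50 (average; 81% instead of 92–93%).

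**Cost of avoiding Baseline 2 in the analysis.** Baseline 1 alone raises the SE by sqrt(0.75/0.667) = 1.06 to sqrt(0.51/0.424) = 1.10. It lowers mean squared error only if delta exceeds sqrt(k(1 − rho²)). For a pairwise contrast k = 2/45, giving 0.18 (rho 0.5) to 0.15 (rho 0.7). For the trend k = 0.05/(45 × 0.04) = 0.0278, giving 0.14 to 0.12. Dropping the urine covariate raises the SE by 1/sqrt(0.75) = 1.15 to 1/sqrt(0.51) = 1.40. It pays only if delta exceeds sqrt(k): 0.21 pairwise, 0.167 for the trend.

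**The case against.** The harm is conditional at several steps. Section 9.1 names only baseline CPD as a covariate; if Aim 2 models carry no own-outcome baseline, the bias is zero. Section 6.3 mentions pods, not the device, and puts the first supervised JUUL trial after the physiological measures. The 1-to-2-day lead can be read as applying to delivery only. The NNAL figure in Section 3.2, a 64% fall, comes from smokers who had switched for two weeks, so it does not support a 0.1 to 0.3 SD shift after a day or two of possible use. The largest ratios need high correlation, large shift and the urine covariate together. For cigarette demand, rho is especially uncertain, because Week 16 adds a study-cigarette version of the task. All of this stands; it limits the weight of the point and leaves the timing flaw in place.

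Three stronger readings are tempting, and the documents support none of them. A reader might infer that participants vape before Baseline 2; that is possible but not shown. A reader might infer that the primary CPD analysis is compromised; the 7-day lock says otherwise, apart from the possible small overlap. A reader might also infer that a primary endpoint is exposed because Section 17 lists dependence severity as primary. That entry names no instrument, and Section 17 places both FTND and WISDM under secondary endpoints.

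One could also read Section 6.3 as a deliberate exception, made for remote training, to the exchange rule in Section 6. That may be the intent, but nothing says so.

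**Conclusion.** The point holds in a limited, conditional form and should be fixed. As written, two of four arms have a Baseline 2 taken after disclosure, and that value is half of the averaged baseline and all of the urine baseline. Whether this biases anything depends on own-baseline adjustment in Aim 2, which is inferred, and on a shift that the documents do not quantify. Under the assumed ranges, pairwise bias is 0.03 to 0.12 SD for averaged measures and 0.05 to 0.21 SD for urine, against a design effect of 0.60 SD; with no shift it is zero. The reach is Aim 2 and the subjective measures, and only contrasts that involve an e-cigarette arm. Psychiatric symptoms are among the exposed measures but carry no tested hypothesis (Section 1).

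**What to change.** **Preferred.** In all four arms, after the 7-day window, complete the Baseline 2 questionnaires (except flavor rating), CO and first-void urine before the condition is disclosed and pods are handed over. Training and flavor rating follow. This loses no precision. Collection kits are already in hand, since participants are "supplied with saliva test equipment and urine collection equipment during the Baseline 1 product exchange". The cost is a later training call or an extra handover for some e-cigarette participants.

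**In Section 9.1.** Name the baseline covariate for each Aim 2 outcome and define it identically in all arms. Do not define baseline as whatever was measured before disclosure: read literally, that gives Baseline 1 alone in the e-cigarette arms and both visits in the others, so ordinary drift between visits would be confounded with condition.

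**If the order cannot change.** Report a sensitivity analysis with Baseline 1 alone in every arm for measures taken at both visits (SE 6–10% larger), and one without the Baseline 2 covariate for urine (SE 15–40% larger). Given the break-even shifts above, neither should replace the main analysis by default.

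**In either case.** Report Baseline 2 minus Baseline 1 by arm for measures taken at both visits. This cannot be done for urine, which has one pre-treatment sample.

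**Text.** Reconcile Sections 4, 6 and 6.1 with Section 6.3 on when assignment, disclosure and handover occur. Section 6.1 allows Baseline 2 at day 7, but pods delivered 1 to 2 days earlier, and only after day 7, cannot fit that minimum.
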